10.1.2.6. Safety analysis

All participants included in the Safety set (SS) will be evaluated by treatment arms unless otherwise specified.

10.1.2.6.1. Adverse events

Treatment-emergent adverse events are defined as any AEs reported from the date of first administration of IMP to 30 days after the last date of IMP. Frequency and percentages of participants will be summarized for: any grade TEAE, Grade 3 or higher TEAE, IMP related TEAE, serious TEAE, TEAE leading to dose modification, TEAE leading to IMP discontinuation, death and TEAE leading to death. Adverse events will be summarized by SOC and preferred term. All AE data will be listed by participant.

Of note, the seriousness and the relationship to the IMP of the adverse event correspond to the investigator opinion or, in case of events upgraded by the sponsor for seriousness or for causality in case of SAE, to the sponsor opinion.

Number and percentage of participants who experienced a DLT will be summarized and listed for Safety Lead-In part.

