Observation requirements: The participants will be observed for a minimum of 2 hours following completion of the first administration of futuximab/modotuximab on C1D1 and a minimum of 1 hour following completion of subsequent infusions of futuximab/modotuximab (C1D8, onward). Participants could be hospitalized for 24 hours after the administration of futuximab/modotuximab per the investigator's discretion and/or local practice per country, to enable a close in-patient safety monitoring. At the end of each infusion, the IV line must remain in place for at least 1 hour to allow administration of IV drugs, if necessary. Futuximab/modotuximab infusions will take place under the close supervision of physician or other study personnel experienced in administration of IV agents and in an environment where full resuscitation facilities are immediately available.
Trifluridine/tipiracil Premedication: Anti-emetic therapy is recommended to prevent nausea and vomiting (Section 6.1.4). Administration schedule: Trifluridine/tipiracil will be administered, before futuximab/modotuximab administration, at a dose 35 mg/m ² /dose, orally twice a day (BID), within 1 hour after completion of morning and evening meals (or in accordance with the local SmPC [Summary of Product Characteristics] of trifluridine/tipiracil), 5 days on/2 days off, over 14 days (2 weeks), followed by a 14-day (2 weeks) rest. This treatment cycle will be repeated every 28-days (4 weeks).
Comparator (Only for Randomised part): The comparator agent (control) is trifluridine/tipiracil. Trifluridine/tipiracil will be administered at a dose 35 mg/m ² /dose, orally BID, within 1 hour after completion of morning and evening meals (or in accordance with the local SmPC of trifluridine/tipiracil), 5 days on/2 days off, over 14 days (2 weeks), followed by a 14-day (2 weeks) rest. This treatment cycle will be repeated every 28-days (4 weeks).
Duration of treatment: Active treatment period: Participants will be treated until they meet a discontinuation criterion (Section 5.8.1). Administration will be at the same dose level (unless dose reduction is necessary) and infusion duration established for the participant during Cycle 1, and on the same weekly schedule provided retreatment criteria are met.

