5.8. Participant withdrawal

5.8.1. Withdrawal criteria

A participant may be withdrawn from the study at any time for any reason (*e.g.* lost to follow-up, withdrawal of consent, AE). Premature discontinuation of IMP does not mean that the participant prematurely stops the participation in the study.

Information to be collected during the last visit of these participants is given in [Section 5.8.2](#). These follow-up modalities are used to ensure the efficacy and safety evaluation of all participants who received IMP.

The reasons for **premature IMP discontinuation** are:

- **Adverse events**, incompatible with continuation of the IMP according to the judgment of the investigator, including no recovery in safety parameters.
- **Pregnancy** (for reporting, see [Section 8.9.2.3](#)).
- **Major protocol deviation** if it interferes with the study evaluations and/or if it jeopardises participant's safety, *e.g.* any medical event requiring administration of an unauthorised concomitant treatment ([Section 6.3](#)).
- **Radiologic progressive disease** documented by CT-scan or MRI.
- **Clinical progressive disease** manifested by symptomatic deterioration.
- **Non-medical reason** (*e.g.* consent withdrawal, participant's removal).
- **Other, physician decision** (for reasons that cannot be included in any of the criteria listed above for example: availability of a better therapeutic alternative for the participant).

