6.1.1.3. Schedule

- Once weekly on Day 1, Day 8, Day 15, and Day 22 (\pm 2 days) of each cycle (4 weeks [28 days] equals 1 dosing cycle).

A weekly dosing schedule is to be maintained, unless delay is required to allow for amelioration of toxicities (or in the event of scheduling difficulties associated with extended weekends, holidays, etc.). Futuximab/modotuximab should be administered after trifluridine/tipiracil intake.

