6.1.3.2. Schedule

- Trifluridine/tipiracil should be administered before futuximab/modotuximab administration.
- Trifluridine/tipiracil should only be given on Days 1 through 5 and Days 8 through 12 of each cycle. If doses are missed or held on those days, the participant should not make up for missed doses. Extension of study treatment into Days 6 to 7 or into the rest period (Days 13 through 28) is not permitted.
- Trifluridine/tipiracil should be taken with a glass of water within 1 hour after completion of morning and evening meals (or in accordance with the local SmPC of trifluridine/tipiracil).
- Any missed doses reported by the participant should be recorded in the e-CRF.
- Trifluridine/tipiracil dosage is calculated according to BSA (Body Surface Area). Table (6.1.3.2) 1 shows the number of tablets that are needed per calculated BSA for a dose of 35 mg/m². Table (6.1.3.2) 2 shows the number of tablets that are needed per calculated BSA for a reduced dose (30 mg/m², 25 mg/m² and 20 mg/m²). The BSA will be calculated by the site (in Safety Lead-In part) or IWRS (in Randomised part) using the following DuBois formula³⁰ all BSA calculations are rounded to 2 decimal places): BSA (m²) = ([Body Weight (kg)]^{0.425} x [Height (cm)]^{0.725}) x 0.007184.
- If at the beginning of the new treatment cycle, a participant's body weight decreases by $\geq 10\%$ from baseline, the site (in Safety Lead-In part) or IWRS (in Randomised part), will recalculate the participant's BSA and adjust trifluridine/tipiracil dosage.
- In case of change of dose level in Randomised part, the IWRS will provide the study site with the adjusted trifluridine/tipiracil dosage.
- No increase in trifluridine/tipiracil dose due to increase in BSA is permitted.

Table (6.1.3.2) 1 - Number of tablets of trifluridine/tipiracil per dose (standard dose) according to body surface area

Trifluridine/tipiracil Dose (2 x daily)	BSA (m ²)	Dosage in mg (2x daily)	Total daily dose (mg)	Tablets per dose (2x daily)	
				15 mg/6.14 mg	20 mg/8.19 mg
35 mg/m ²	< 1.07	35	70	1	1
	1.07 - 1.22	40	80	0	2
	1.23 - 1.37	45	90	3	0
	1.38 - 1.52	50	100	2	1
	1.53 - 1.68	55	110	1	2
	1.69 - 1.83	60	120	0	3
	1.84 - 1.98	65	130	3	1
	1.99 - 2.14	70	140	2	2
	2.15 - 2.29	75	150	1	3
	≥ 2.30	80	160	0	4

BSA = body surface area (calculate to 2 decimal places)

Table (6.1.3.2) 2 - Number of tablets of trifluridine/tipiracil per dose (reduced dose) according to body surface area

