10.1.2.8. Interim analysis

There are 3 planned interim analyses: an early futility interim analysis (interim 0) will be triggered when ~ 83 PFS events have been observed in DN population which is designed under a hypothetical Phase 2 study that would have 95% power to detect a true hazard ratio for PFS of $HR \leq 0.525$ (assumptions of mPFS 4 months *versus* 2.1 months) with a one-sided alpha level of 0.10. This futility analysis will use both PFS and OS data to calculate the Predictive Probability of Success incorporating historical data based on an extension of the methodology proposed by Saint Hilary *et al.*⁴⁰ for decision making. More details on the methodology and PPos calculation will be provided in SAP. Study will be stopped for futility if the calculated PPos $< 10\%$. If the study proceeds, an interim OS analysis for futility (interim 1) will be conducted when approximately 33.3% of the planned final number of OS events in DN population (*i.e.* 128 of 383 OS events) have been observed. If the study proceeds, a second interim analysis will occur to evaluate futility and efficacy (interim 2) when 255 events (66.7% of the planned final number of OS events) have occurred in DN population.

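### The Randomised part's between-arm safety comparison rests only on crude TEAE percentages over a window that follows treatment duration, which can favour Arm B by up to about 13 points if the plan's PFS assumption holds

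*Protocol*

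**What the plan says.** The synopsis, Table (3.4) 2 and Protocol 10.1.2.4.2 make comparison of the two arms' safety profiles a secondary objective of the Randomised part.

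For adverse events, Protocol 10.1.2.6.1 specifies proportions: "Frequency and percentages of participants will be summarized for: any grade TEAE, Grade 3 or higher TEAE", followed by further categories (related, serious, leading to dose modification or discontinuation, death). An event is treatment-emergent if reported "from the date of first administration of IMP to 30 days after the last date of IMP".

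Treatment has no fixed length. The synopsis and 4.1.1 state: "Participants will be treated until they meet a discontinuation criterion". Protocol 5.8.1 lists, among other reasons, "Radiologic progressive disease documented by CT-scan or MRI".

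The only arm-specific PFS figures in the plan are in 10.1.2.8, for the early futility look: "assumptions of mPFS 4 months" against 2.1 months.

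The dosing calendars differ. The antibody is given "Once weekly on Day 1, Day 8, Day 15, and Day 22" of each cycle. Trifluridine/tipiracil "should only be given on Days 1 through 5 and Days 8 through 12 of each cycle".

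Protocol 10.1.2.3 describes exposure (cycles, cumulative dose, dose intensity) separately and does not link it to event incidence. The protocol specifies no exposure-adjusted rate, time-to-first-event analysis or fixed-day incidence for adverse events. It plans no formal test of them either.

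**The concern.** A crude percentage depends on the event hazard and on how long each participant is watched. Here the watching time is an outcome of treatment. If the antibody delays progression, Arm A participants stay on treatment longer and have more time to record a first event, even when the hazard per month is the same in both arms.

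Toxicity of the shared trifluridine/tipiracil backbone could then be read as excess toxicity of the antibody, and the better the disease control, the larger that apparent excess. The DMC reviews safety and can recommend modifying or stopping the study (Protocol 8.10), and the same tables would feed the benefit-risk account.

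A second, smaller asymmetry comes from the calendar. In a completed cycle the last IMP falls on Day 22 in Arm A and Day 12 in Arm B, so the 30-day tail closes on Day 52 in Arm A and Day 42 in Arm B.

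**Working it through.** **Plan's own figure first.** The early futility look needs about 83 PFS events for HR 0.525, 95% power and one-sided alpha 0.10. Schoenfeld's formula gives 4 × (1.2816 + 1.6449)² / (ln 0.525)² = 4 × 8.564 / 0.4152 = 82.5, so 83. Also 2.1/4 = 0.525. The exposure contrast used below is therefore the one in the plan.

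**Inputs from the documents.** Median PFS m = 4 months (Arm A) and 2.1 months (Arm B), from 10.1.2.8. Tail of 30 days, from 10.1.2.6.1. Month of 30.44 days, from SAP 5.1.3, so w = 30/30.44 = 0.986 months.

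**Assumptions not in the documents.** Time on treatment is exponential with median equal to PFS. The first-event hazard h is constant and equal in both arms. Everyone contributes the full 30-day tail.

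**At-risk time.** The mean is m/ln 2 + w.
- Arm A: 5.77 + 0.99 = 6.76 months.
- Arm B: 3.03 + 0.99 = 4.02 months.
- Ratio: 1.68.

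**Crude incidence.** With λ = ln 2/m (0.173 in Arm A, 0.330 in Arm B), P(event) = 1 − exp(−h·w) × λ/(λ + h).

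| Hazard per month | Arm B | Arm A | Spurious gap (points) |
|---|---|---|---|
| 0.05 | 17.3% | 26.1% | 8.8 |
| 0.10 | 30.5% | 42.5% | 12.1 |
| 0.20 | 48.9% | 61.9% | 13.0 |

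**Gap by Arm B incidence** (solving for h):

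| Arm B | 1% | 5% | 10% | 20% | 30% | 40-50% | 70% | 80% | 90% | 95% |
|---|---|---|---|---|---|---|---|---|---|---|
| Gap (points) | 0.7 | 3.1 | 5.8 | 9.7 | 12.0 | 13.0 | 10.0 | 7.3 | 4.0 | 2.1 |

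The maximum is 13.1 points at an Arm B incidence of 44%. The gap is 9 points or more between about 18% and 74%. Protocol 2.8 quotes trifluridine/tipiracil rates of 53% for neutropenia (34% at Grade 3 or above). As Arm B rates these give 12.7 and 12.6 points.

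**When the constant hazard fails.** Events confined to the first month give a gap of 0. Events confined to the first three months give about 2-4 points.

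**When the PFS contrast is smaller.** At 3 vs 2.1 months the largest gap on the grid examined is 7.1 points. At 2.7 vs 2.6 months, the phase 2 PFS of the 9/6 regimen and its control (Protocol 2.2.2), it is under 1 point. At equal exposure it is 0.

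**Last-dose day.** If every last cycle is completed, the Arm A tail is effectively 40 days, so w = 40/30.44 = 1.314. At hazards 0.05, 0.10 and 0.20 this adds 1.2, 1.9 and 2.4 points to the gaps above. With PFS equal at 2.1 months in both arms it leaves 1.4, 2.3 and 3.3 points by itself.

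**Does the remedy work?** Mean person-time to first event or end of window is (1 − exp(−h·w))/h + exp(−h·w)/(λ + h). At h = 0.10 this is 4.254 months in Arm A and 3.046 in Arm B. The rates are 0.4254/4.254 and 0.3046/3.046, both 0.100 per month. The spurious difference disappears in this model.

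**The case against.** A reader might infer that Arm A would show 9-13 points more events as a general result, even with no drug effect. The documents do not support that. With no drug effect the treatment-duration part of the gap is zero. It needs a real PFS benefit, and the claim can only be that there is no effect on the event hazard. Nor is the range general: near-universal categories (any-grade TEAE may be one), rare ones and early-onset toxicity show far less.

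The exposure contrast can also be challenged. The 4 vs 2.1 months come from a hypothetical phase 2 design for the futility look and are PFS, not time on treatment. Participants also stop for toxicity or consent withdrawal, and may drop one agent and continue the other (Protocol 5.8.1, 8.11). Dose reduction after cytopenia makes a constant hazard doubtful. All of this stands, and it makes the size conditional.

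Disease symptoms are a weak example of misread events, because Protocol 8.3 largely excludes findings of the studied disease from AE reporting. That stands too; backbone toxicity is the relevant case.

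The protocol leaves implementation detail to the SAP (10.1). SAP v2.0 has removed the Randomised-part methods and v1.0 is not available, so adjusted rates may once have been planned there. What can be said is that the protocol does not specify them. The comparison is descriptive and exposure would be tabulated nearby, which helps a careful reader but does not adjust the percentages.

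**Conclusion.** The point holds in a conditional form. A stated comparative objective is served in the protocol only by crude percentages over a window tied to treatment duration, and the plan's own PFS assumption makes that window about 1.7 times longer on average in Arm A.

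The resulting bias is up to about 13 points for mid-frequency events and much smaller elsewhere. It rests on 4 vs 2.1 months being true, time on treatment following PFS, and a constant, equal hazard. The last-dose-day asymmetry of about 1-3 points does not need a PFS difference, but it assumes completed last cycles.

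A reader might also infer that reported results are affected. They are not: SAP section 1 records that the Randomised part was cancelled, and SAP v2.0 covers a single-arm lead-in with no between-arm comparison. The point matters for Protocol 10.1.2.6.1 as written and for any reuse of this design.

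**What to change.** Keep the crude percentages and the TEAE window as defined. Add two analyses to Protocol 10.1.2.6.1 for the between-arm comparison:

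1. **Exposure-adjusted first-event rates.** Participants with an event per 100 patient-months, with person-time ending at the first event, death, data cut-off or last IMP + 30 days, whichever is earliest. Report the rate difference with a 95% CI.
2. **Cumulative incidence at a fixed day,** for example Day 84, with death as a competing event and participants censored when their AE collection ends. The censoring rule matters: by Day 84, (84 − 30)/30.44 = 1.774 months, the model has 1 − exp(−0.330 × 1.774) = 44% of Arm B and 1 − exp(−0.173 × 1.774) = 26% of Arm A already out of the window.

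Do not try to equalise the arms by closing both windows at first intake of the last cycle + 27 + 30 days. That is Day 58, while Protocol 8.9.1 stops general AE collection 30 days after last IMP (Day 52 in Arm A, Day 42 in Arm B after a completed cycle), apart from related serious events. It would add 6 uncollected days in Arm A and 16 in Arm B, so the 10-day asymmetry would return as under-ascertainment.

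The cost is a few extra tables from dose and event dates already collected. The rates rely on a constant-hazard approximation, which the fixed-day incidence complements. Censoring at the end of AE collection may be informative, since many participants leave because of progression, and this should be stated with the results.

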10.1.2.6.2. Clinical laboratory evaluation

For haematological, biochemistry, urinary and coagulation parameters, descriptive statistics on value at baseline, on value at each post-baseline visit under treatment, on last post-baseline value under treatment and, on change from baseline to last post-baseline value under treatment will be provided.

For all clinical laboratory parameters (except urinary parameters), the following analysis will be performed: Laboratory parameters classified (number and percentage of participants in each class) according to these reference ranges and using shift tables from baseline to the worst (high and/or low) values under treatment.

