	
To further evaluate and to compare the safety profile of futuximab/modotuximab in combination with trifluridine/tipiracil versus trifluridine/tipiracil monotherapy
 
To compare Quality of life (QoL) of futuximab/modotuximab in combination with trifluridine/tipiracil versus trifluridine/tipiracil monotherapy
 
To characterise the pharmacokinetic (PK) profile of futuximab/modotuximab, trifluridine and tipiracil in the combination futuximab/modotuximab with trifluridine/tipiracil
 
To further evaluate the immunogenicity of futuximab/modotuximab (i.e. occurrence of antidrug antibody [ADA])
	
 - Incidence, severity and relationship of TEAEs and STEAEs collected from administration of the first dose of IMPs - AEs leading to dose interruption, dose delays and permanent treatment stop - Changes from baseline in key laboratory safety assessments, and vital signs - QoL is assessed by 2 questionnaires European Organization for Research and Treatment of Cancer (EORTC) QLQ-C30 and EQ-5D-5L - Derived PK parameters (e.g. Cmax, AUC) for futuximab/modotuximab, trifluridine and tipiracil 
ADA development for futuximab/modotuximab

Exploratory	
To explore the PK/pharmacodynamic (PD) relationship for safety and/or efficacy of the combination futuximab/modotuximab with trifluridine/tipiracil
 
To explore biomarkers as potential predictors of response and to track the emergence of resistance
	
 - Relationship between exposure and PD (as safety and efficacy) - Circulating tumour DNA (CtDNA) monitoring

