 - b. Treatment period: tumour assessments will be done every 8 weeks from C1D1 (\pm 7 calendar days) until radiologic progression is documented
 - c. Withdrawal visit: tumour assessments will be performed only if not performed within previous 8 weeks. Every effort should be made to perform the WV tumour assessments prior to the start of new anti-cancer therapy.
 - d. Follow-up period: unless patient had discontinued study treatments for radiologic disease progression or withdrawal of consent, obtain tumour assessments within 8 weeks after the last previous tumour assessment and then every 8 weeks (\pm 10 calendar days) until documentation of radiologic disease progression, regardless of initiation of a new anticancer therapy
7. Vital signs, including body temperature, pulse rate, respiratory rate, blood pressure, oxygen saturation by pulse oximetry
8. Study procedures prior to the first study treatments administration: to be done at C1D1 prior to study treatments administration only if baseline procedures have been done more than 7 days prior to C1D1
9. Study procedures obtained within 48 hours prior to study treatments administration (trifluridine/tipiracil intake in Arm B of Randomised part on CXD1)
10. To be performed only for futuximab/modotuximab participants (Arm A)
11. Pregnancy testing
 - a. Pregnancy testing at screening period: with serum β HCG test only (Within 7 days prior to first administration of first IMP)
 - b. Pregnancy tests should be performed at the beginning of each cycle during the treatment period, upon treatment discontinuation, at the first follow-up visit, and additionally if clinically indicated, for all relevant patients. More frequent pregnancy tests should be performed if required by local law or as clinically indicated.
12. ECG assessment: To include standard 12-lead ECG with measurement of PR interval, QRS duration, time from the beginning of the QRS complex, representing ventricular depolarization, to the end of the T wave, resulting from ventricular repolarization (QT) interval, and QTc interval [ms], as well as heart rate [beats per minute (BPM)]

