8.2.7. Laboratory Assessments

Laboratory tests will be collected and analysed by the study site's certified laboratory during screening period and at C1D1 only if there is more than 7 days since screening assessment. In all cases, the full validated set of normal ranges values will be collected, as well as any update in these values during the study and must be documented on the corresponding page of the e-CRF.

It is preferable for all biochemistry blood samplings to be taken in fasting conditions except if the participant's general health status does not permit it.

Laboratory tests are to be performed as required per protocol. All laboratory values that are out of the normal range are to be evaluated for their clinical significance before exposing the participant to the next dose of study medication.

Any laboratory abnormality that has a clinical impact on the participant, *e.g.*, results in delay of study medications dosing, study discontinuation, requires treatment due to abnormal values, or is considered by the investigator to be medically important, must be reported as an AE, unless it is considered a supporting analysis to a clinical diagnosis that is already reported as an AE.

All laboratory data will be analysed using NCI-CTCAE grade criteria (version 5.0).

Repeat the evaluation of any clinically significant laboratory test, as clinically indicated, until the value returns to the baseline level or clinically stabilises, or until another treatment is given.

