8.2.7.2. Biochemistry

Samples for biochemistry assessments to be collected at the following time points:

- Inclusion
- Cycle 1
 - C1D1 (Pre-dose*)
 - C1D15 (Pre-dose**)
- All subsequent cycles
 - CxD1 (Pre-dose**)
 - CxD15 (Pre-dose**)
- WV

- As clinically indicated

**Study procedures prior to the first study treatments administration: to be done at C1D1 prior to study treatments administration only if baseline procedures have been done more than 7 days prior to C1D1.*

***Study procedures obtained within 48 hours prior to study treatments administration (only for CxD1: trifluridine/tipiracil intake in Arm B of Randomised part).*

Measure the following serum biochemistry parameters: albumin, ionogram (sodium, potassium, chloride, total calcium, magnesium, phosphate), blood urea nitrogen (BUN), serum creatinine, glucose, AST (SGOT), ALT (SGPT), GGT, alkaline phosphatase, total bilirubin (in case of elevation in total bilirubin, fractionation (direct/indirect) should be performed), LDH.

Note: If BUN is not available, use the following conversion:

Table (8.2.7.2) 1 - Correspondence between urea and BUN values

BUN (mmol/L) = UREA (mmol/L)
BUN (mg/dL) = UREA (mg/dL) x 0.467
BUN (mg/dL) = UREA (mmol/L) / 0.3571

8.2.7.3. Serum Magnesium, Calcium, and Potassium (Only for futuximab/modotuximab-treated participants (Safety Lead-In part and Arm A of Randomised part)

Samples for serum magnesium, total calcium, and potassium assessment to be collected at the following time points:

- Cycle 1:
 - C1D8 (Pre-dose*).
 - C1D22 (Pre-dose*).
- All subsequent cycles:
 - CxD8 (Pre-dose*).
 - CxD22 (Pre-dose*).
- As clinically indicated**.

**Study procedures obtained within 48 hours prior to study treatments administration*

*** An ECG should be performed in the event of \geq Grade 3 hypomagnesemia and if otherwise clinically indicated.*

Timepoints shown are in addition to testing performed as part of scheduled biochemistry panels; intention is to achieve weekly magnesium, total calcium, and potassium testing during the treatment period.

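### In the planned Randomised part, magnesium, calcium and potassium are scheduled four times per cycle in Arm A and twice in Arm B, so worst-value shift tables by arm would tend to show more abnormality in Arm A even with no drug effect

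*Protocol*

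**What the plan says.** Table (3.4) 2 of the protocol makes the safety comparison a secondary objective of the Randomised part: "To further evaluate and to compare the safety profile of futuximab/modotuximab in combination with trifluridine/tipiracil" against trifluridine/tipiracil alone.

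Section 8.2.7.2 puts the three electrolytes in the routine panel of both arms ("ionogram (sodium, potassium, chloride, total calcium, magnesium, phosphate"). The panel is taken on D1 and D15 of each cycle (the latter listed as "CxD15 (Pre-dose") and at the withdrawal visit.

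Section 8.2.7.3, headed "Serum Magnesium, Calcium, and Potassium (Only for futuximab/modotuximab-treated participants (Safety Lead-In part and Arm A of Randomised part"), adds D8 and D22. It explains that the "intention is to achieve weekly magnesium, total calcium, and potassium testing during the treatment period". In Table (4.1.2) 2 the Mg/Ca/K row carries footnote 10: "To be performed only for futuximab/modotuximab participants (Arm A"). Appendix 12 gives the same counts: two biochemistry samples plus two additional Mg/Ca/K samples per cycle.

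Section 10.1.2.6 presents safety by treatment arm in the Safety Set. Section 10.1.2.6.2 classifies all laboratory parameters except urinary ones by reference range, "using shift tables from baseline to the worst (high and/or low) values under treatment". It does not limit the worst value to visits that both arms share. The same section also plans summaries at each visit, of the last value, and of change to the last value.

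SAP v2.0, section 1, states that the Randomised part was cancelled. That SAP analyses one treatment group.

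**The concern.** The worst of four values per cycle cannot be better than the worst of two of those four. If both arms have the same distribution of electrolyte values, the arm sampled more often will therefore tend to show more participants in the abnormal classes of the shift table. Criterion 19a requires potassium and magnesium within normal limits at entry, so for these two the table is close to a count of participants who were ever abnormal. That count depends directly on how often one looks.

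A reader comparing the arms would then see drug effect and monitoring intensity mixed together. For magnesium this matters less, because a large effect is expected: hypomagnesaemia was 56.0% on the 9/6 mg/kg regimen against 7.7% in the control arm of the earlier phase 2 study (section 2.2.2). For potassium and calcium, where the effect may be modest, a difference caused by sampling could be read as toxicity.

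**Working it through.** **Step 1: count scheduled samples.** Arm A has D1 + D15 (panel) + D8 + D22 (extra) = 4 per 28-day cycle, which matches the protocol's stated aim of weekly testing. Arm B has D1 + D15 = 2 per cycle. C1D1 is pre-dose and serves as baseline, so over k cycles the post-baseline counts, including the withdrawal visit, are:

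- Arm A: 3 + 4(k − 1) + 1 = 4k
- Arm B: 1 + 2(k − 1) + 1 = 2k

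This gives 8 against 4 for 2 cycles, 16 against 8 for 4 cycles, and 28 against 14 for 7 cycles. Without the withdrawal visit the counts are 7 against 3, 15 against 7, and 27 against 13. Seven cycles corresponds to the synopsis figure of about 6.5 months of treatment: 6.5 × 30.44 / 28 = 7.07.

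**Step 2: chance of at least one abnormal value with no drug effect.** Let p be the chance that a single sample is abnormal, equal in both arms, and m the number of samples. For independent samples:

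P(ever abnormal) = 1 − (1 − p)^m

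For p = 1% and 2 cycles: Arm A 1 − 0.99^8 = 7.7%; Arm B 1 − 0.99^4 = 3.9%. For p = 2.5% and 7 cycles: Arm A 1 − 0.975^28 = 50.8%; Arm B 1 − 0.975^14 = 29.8%.

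**Step 3: allow for correlation within a participant.** Electrolyte values in one person are not independent, so two other models were used, both on a normal scale with the abnormality threshold set to give p per sample.

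- Random intercept with intraclass correlation ρ: average over a standard normal u of 1 − [1 − Φ((Φ⁻¹(p) − √ρ·u)/√(1 − ρ))]^m.
- Weekly first-order autoregression, simulated with 200,000 participants; Arm A is seen every week and Arm B every second week.

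Selected results, equal time on treatment in both arms:

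| Model | p | Cycles | Arm A | Arm B | Ratio |
|---|---|---|---|---|---|
| Independent | 1% | 2 | 7.7% | 3.9% | 1.96 |
| Independent | 2.5% | 7 | 50.8% | 29.8% | 1.70 |
| Intraclass correlation 0.5 | 2.5% | 2 | 12.5% | 7.8% | 1.61 |
| Intraclass correlation 0.5 | 2.5% | 7 | 24.7% | 17.4% | 1.42 |
| Intraclass correlation 0.8 | 2.5% | 7 | 12.5% | 9.9% | 1.27 |
| Weekly autocorrelation 0.8 | 2.5% | 7 | 29.1% | 21.8% | 1.33 |
| Weekly autocorrelation 0.95 | 2.5% | 7 | 13.8% | 11.9% | 1.16 |
| Weekly autocorrelation 0.95 | 5% | 7 | 23.2% | 20.4% | 1.14 |

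Over every combination tried (p from 1% to 5%; 2, 4 and 7 cycles), the ratio ran from 1.14 to 1.96. The values of p and the correlations are assumptions; the documents give neither.

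**Step 4: restrict to shared visits.** With D1, D15 and the withdrawal visit only, both arms have 2k values. At p = 2.5% and 7 cycles the expected proportions become 29.8% in both arms (independent) or 17.4% in both (intraclass correlation 0.5).

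**Step 5: what the restriction does not do.** Suppose, purely for illustration, 4 cycles in one arm, 2 in the other, and p = 2%. Shared visits then give 8 samples against 4: 1 − 0.98^8 = 14.9% against 1 − 0.98^4 = 7.8%. Unequal time on treatment needs separate handling.

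**The case against.** The strongest reply is that no such table will be produced. The Randomised part was cancelled and SAP v2.0 has a single group. That stands: the point concerns the protocol's plan and any reuse of this design. The protocol also left implementation detail to the SAP, and the version available no longer contains the randomised methods, so whether an earlier SAP dealt with this cannot be seen.

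Second, the same protocol section already gives summaries that are not extremes over unequal numbers of samples. This also stands. By-visit values at D1 and D15 compare like with like, and a reader who inferred that the laboratory comparison as a whole is invalid would be going too far. The by-visit tables do not, however, count participants who were ever abnormal, which is the purpose of the worst-value table. The tables are descriptive; no hypothesis test is planned for them.

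Third, weekly detection in Arm A can lead to earlier repletion under Appendix 11 and so to shallower nadirs. The calculation does not model this. The direction is therefore a tendency under no drug effect and not a certainty for observed data.

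Several stronger readings are tempting but not supported:

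- A reader might infer a doubling. The ratio comes close to 2 only with independent samples and a low p.
- A reader might take the medians of 4 and 2.1 months in section 10.1.2.8 as planned treatment durations. They are PFS assumptions for the interim 0 futility design; the only stated treatment duration, about 6.5 months, does not differ by arm.
- A reader might conclude that TEAE percentages are inflated to the same extent. Under section 8.2.7 a laboratory abnormality that, for example, "requires treatment due to abnormal values, or is considered by the investigator to be medically important, must be reported as an AE", but the rule covers abnormalities with clinical impact. Most isolated out-of-range values would not qualify, and the documents give no basis for sizing any carry-over.
- Section 8.12.6 mentions weekly monitoring without naming an arm. Section 8.2.7.3, the schedule footnote and Appendix 11 limit it to futuximab/modotuximab participants.

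**Conclusion.** The point holds as a modest flaw in the protocol's plan for the Randomised part. The 4-to-2 sampling and the use of the worst value by arm are both in the text, and nothing in it reconciles them. With no drug effect and equal time on treatment, Arm A's proportion ever abnormal for Mg, Ca or K would tend to be about 1.1 to 2 times Arm B's, depending on an assumed per-sample rate and within-participant correlation. With realistic correlation the lower part of that range is more plausible. The effect is confined to one type of table and three analytes, and matters mainly for potassium and calcium. It is a cheap improvement to a stated secondary objective, and it does not affect the lead-in analysis under SAP v2.0.

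**What to change.** For the between-arm Mg, Ca and K worst-value shift tables, use only samples scheduled in both arms: D1, D15 and the withdrawal visit. Show the all-samples tables separately, so that no Arm A nadir is hidden.

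Because this does not correct for unequal time on treatment, also limit the between-arm table to a common window (for example the first 2 cycles) or report it per patient-month. The interim 0 PFS medians should not be cited as planned treatment durations in support of this.

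The cost is one extra table programme and a few sentences of analysis wording. The downside is that the restricted table may miss some true nadirs, which the all-samples table still shows. The monitoring schedule stays as it is.
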